2.2 Violations and deviations

Subjects will be assessed by comparison of their electronic case report form (eCRF) data with the criteria below; protocol waivers will not be taken into consideration (e.g. if a subject younger than 18 enters the study on a protocol waiver, the subject would still be excluded from the PPS).

The following criteria may be considered as important protocol deviations which have a major effect on efficacy or that could potentially affect the interpretability of the study results and which should lead to exclusion from the PPS.

- Subjects who failed any of the inclusion or exclusion criteria of the study.
- Inappropriate compliance with study treatment during the randomized placebocontrolled phase of the study, e.g. treatment compliance of less than 80% or greater than 120%
- All prohibited medications which are administered during the randomized placebocontrolled phase of the study. Prohibited medications include patients starting on renin-angiotensin-aldosterone system inhibitor (RAASi) therapy during the trial Note: RAASi therapies: Angiotensin-converting enzyme inhibitor (ACEi), angiotensin II receptor blocker (ARB) or angiotensin receptor-neprilysin inhibitor (ARNi) are permitted to be continued at the same dose as baseline.
- Errors in treatment allocation. Any subject who received incorrect study treatment compared with randomized study treatment at any time during the study
- Any subject unblinded during the study
- Rules for rescue medication for hyperkalemia or metabolic acidosis violated
- Start of double-blind study medication prior to randomization date
- Subject with first dose prior to baseline evaluations.

In addition, protocol deviations will be defined by the Sponsor before database lock as coronavirus disease 2019 (COVID-19) pandemic related or not by judging the root cause of the protocol deviation, in line with FDA guidance (FDA Guidance on Conduct of Clinical Trials of Medical Products during COVID-19 Public Health Emergency; March 2020). The following criteria may be considered as indicative of a protocol deviation related to the COVID-19 pandemic.

- Missed in-person visit due to COVID-19 illness and/or COVID-19 public health control measures
- Study visit out of window due to COVID-19 illness and/or COVID-19 public health control measures
- Missed doses due to COVID-19 illness and/or COVID-19 public health control measures
- Missed sK+ measurements due to COVID-19 illness and/or COVID-19 public health control measures
- Missed bicarbonate measurements due to COVID-19 illness and/or COVID-19 public health control measures

2.3 Analysis Periods

Analysis periods defined in this section are distinct from those used to describe the study design in the CSP and section 1.2 of the SAP.

Screening Period

The screening period is defined as the period from informed consent to the first dose of openlabel study or screen failure.

Open-label correction period

The open-label correction period refers to the period from first dose of open-label study treatment to the earliest date of randomization, withdrawal of consent, last contact with the subject or death.

Randomized placebo-controlled period

The randomized placebo-controlled period refers to the period from randomization to the earliest date of rescue treatment for hyperkalemia or low serum bicarbonate, last assessment during follow-up (day 36 ± 3), withdrawal of consent, last contact with the subject, or death.

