1.2 Study design

This is a prospective, randomized, double-blind, placebo-controlled, parallel, multicenter, Phase IIIb study to investigate the safety and efficacy of SZC in patients with hyperkalemia and low bicarbonate (or metabolic acidosis).

The study will be conducted in the United States (US) at approximately 35 investigative sites.

This study consists of a short screening visit (Day 1), an open-label correction period (up to 48 hours), a 4-week randomized treatment period, and a follow-up period (7 days after the last administration of study medication). The total study treatment duration, consisting of open-label and randomized periods, will be 29 days.

Screening will be performed using potassium and bicarbonate value from a study-approved point-of-care test (POCT) to determine eligibility of consenting patients to enter the openlabel correction phase. Patients who meet the POCT eligibility criteria of serum potassium (sK+) between 5.1-5.9 mmol/L inclusive, AND serum bicarbonate between 16-20 mmol/L inclusive, will be enrolled into the open-label correction phase. All baseline parameters should be measured/collected prior to administration of the first dose of study drug in the open-label initial phase.

In the open-label initial phase, patients will receive open-label SZC orally at a dose of 10 g three times daily (TID) for up to 48 hours, depending on POCT potassium value.

Patients who achieve normokalemia (K+ between 3.5 and 5.0 mmol/L inclusive) within 24-48 hours will be randomized 1:1 into the double-blind randomized treatment phase to receive 10 g SZC or placebo once daily (QD) starting dose for the following 28 days. Patients who achieve normokalemia after 24 hours will be randomized and will not need to continue on 10 g SZC TID for another 24 hours.

Study treatment will end with the Day 29 visit, which will be followed by the end of study visit 7 days after the last administration of study medication.

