3 PRIMARY AND SECONDARY VARIABLES

3.1 Time Points and Visit Windows

For all populations, assessments will be assigned to visits and analysis periods for categorical summaries as follows:

- Assessments with missing data and assessments marked "Not Done" will be considered as providing a missing response and are not permitted to be assigned to a visit window.
- The worst value (e.g. out of reference range preferred to within range; abnormal preferred to normal) will be used in each window. If multiple assessments fall within the same window with equal value, then the first non-missing will be used for the summary.

Scheduled day and visit window during the open-label period in Table 1 are with respect to the first dose of open-label study treatment. Baseline is defined as measurements taken at the screening visit on day 1 of the study.

Visit	Scheduled Day of Visit	Analysis Period	Protocol Visit Windows	Visit title in TFLs	Analysis Visit Windows
Visit 1	1	Screening/ Open-Label	Day 1	Visit 1 (Baseline)	Day 1
Visit 2	2	Open-Label	Day 2*	Visit 2	Day 2*
Visit 3	2 or 3	Randomized	Days 2 – 3*	Visit 3 (Randomization)	Days 2 – 3*
Visit 4	8	Randomized	Days 7 – 9	Visit 4	Days 4 – 11
Visit 5	15	Randomized	Days 14 – 16	Visit 5	Days 12 – 18
Visit 6	22	Randomized	Days 21 – 23	Visit 6	Days 19 – 25
Visit 7	29	Randomized	Days $28 - 30$	Visit 7 (EOT)	Days 26 – 32
Visit 8	36	Randomized	Days 33 – 39	Visit 8 (Follow-up)	Days 33 - 39

 Table 1 Definition of visit windows

* Assessments conducted on day 2 and day 3 will be assigned to visit 2 or 3 based on the nominally entered visit on the eCRF.

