4.2.7.1 Primary Efficacy Analysis

The primary efficacy endpoint is the occurrence (yes/no) of patients having normal sK+ (between 3.5 and 5.0 mmol/L inclusive) on Day 29 (Visit 7) without rescue treatment for hyperkalemia at any point during the randomized phase in the SZC versus placebo arm. Patients with missing sK+ will have these imputed as described in section 3.3.1. The number and percentage of subjects who achieved a response (Yes, No, Non-evaluable) will be summarized by randomized treatment group in the FAS.

The occurrence will be compared between treatment groups in the FAS using a logistic regression model (excluding non-evaluable responses) including response as the dependent variable and randomized treatment as an independent factor, it will be tested using a two-sided

alpha = 0.05. The common odds ratio will be derived together with the two-sided 95% confidence interval.

Documentation will be provided to check the underlying assumptions for the logistic regression model. Standardized residuals will be presented in a scatter plot by alphanumerical subject ID. Subjects with standardized residuals > 3.0 will be listed. Influential observations on the regression coefficients will be detected by calculating Cook's D statistic (In SAS applied with proc reg with the plots=cooksd option) and presented in a diagnostic plot by alphanumerical subject ID. Subjects with Cook's D statistic > 4/sqrt(n) will be listed.

Estimand Attributes

In line with ICH E9 (R1) addendum, 5 attributes (treatment, population, endpoint, intercurrent events, and population-level summary) have been specified to translate the primary and key secondary efficacy objectives into treatment effects that are to be estimated (estimands).

Endpoint:

• Hyperkalaemia response, defined as an observed sK+ within 3.5-5.0 mEq/L at Day 29 (Visit 7)

Population:

• All subjects who achieve normokalemia at the end of the open-label correction phase, and are randomized

Treatment:

• SZC or Placebo. Patients with $sK+ \ge 6.0 \text{ mmol/L}$ will be managed with rescue therapy employing local standard of care.

Intercurrent Event Strategy:

- Discontinuation of treatment (Treatment policy strategy, i.e. regardless of the intercurrent event)
- Use of rescue therapy for hyperkalaemia at any point during the randomized placebocontrolled period (Composite variable strategy, i.e. considered to be non-response).

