- Use of rescue therapy for low bicarbonate at any point during the randomized placebocontrolled period (Treatment policy strategy, i.e. regardless of the intercurrent event).
- Death prior to Day 29 (Visit 7) (Composite variable strategy, i.e. considered to be non-response).
- Subject lost to follow-up prior to Day 29 (Visit 7) (Hypothetical strategy, i.e. assume response is not evaluable).
- Subject with no sK+ or POCT K measurement at visit 6 or visit 7 (Hypothetical strategy, i.e. assume response is not evaluable).

Population Level Summary:

• Odds ratio of the proportion of responders in the SZC treatment group compared to the placebo group.

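### The randomized analysis period in SAP section 2.3 runs past the end of treatment and closes at the first rescue of either kind, so the primary endpoint and secondary endpoint #7 have no consistent window for counting rescues

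*SAP*

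**What the plan says.** Section 2.3 runs the randomized placebo-controlled period "from randomization to the earliest date of rescue treatment for hyperkalemia or low serum bicarbonate, last assessment during follow-up (day 36 ± 3", with withdrawal of consent, last contact and death as further closing events. It adds: "Analysis periods defined in this section are distinct from those used to describe the study design in the CSP and section 1.2 of the SAP".

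The design in section 1.2 has "a 4-week randomized treatment period, and a follow-up period (7 days after the last administration of study medication" as separate parts, and states: "Study treatment will end with the Day 29 visit, which will be followed by the end of study visit 7 days after the last administration". Table 1 in section 3.1 nevertheless places "Visit 8 (Follow-up"), Days 33 to 39, in the Randomized analysis period.

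The primary estimand in section 4.2.7.1 uses the section 2.3 name twice:
- Hyperkalaemia rescue: "Use of rescue therapy for hyperkalaemia at any point during the randomized placebocontrolled period (Composite variable strategy, i.e. considered to be non-response".
- Low-bicarbonate rescue: "Use of rescue therapy for low bicarbonate at any point during the randomized placebocontrolled period (Treatment policy strategy".

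Secondary endpoint #7, need for low-bicarbonate rescue, is defined over the same named period, and its estimand handles hyperkalaemia rescue by treatment policy. Section 1.1 and the opening of section 4.2.7.1 instead express the rescue condition over the *randomized phase*. Section 3.3.1 uses the Visit 7 potassium provided hyperkalaemia rescue medication has not been used, and gives no window.

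**The concern.** The period that decides which rescues count does not match the question the endpoints ask.

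It is too long at the end. The primary question concerns potassium at Day 29 on treatment, but rescues in the off-drug week count as failures. Only the SZC arm stops an active drug at Day 29, so any resulting shift is more likely to go against SZC. Off-drug low-bicarbonate rescues would also count as #7 events.

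It can also be too short. A treatment-policy event is one after which follow-up continues unchanged. Here a low-bicarbonate rescue ends the period in which hyperkalaemia rescues are counted, and a hyperkalaemia rescue ends the period in which #7 events are counted.

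Two programmers working from this SAP could therefore classify the same patient differently on the primary endpoint.

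**Working it through.** **Step 1. Where the section 2.3 name is used.**
- Exact name: both rescue bullets of the primary estimand, the low-bicarbonate bullet of primary sensitivity analysis (iii), and the definition of endpoint #7.
- Other labels, none defined: *placebo-controlled period* (hyperkalaemia bullets of #1 to #7), *randomized controlled period* (low-bicarbonate bullets of #1 to #6), *randomized-withdrawal period* (hyperkalaemia bullet of sensitivity analysis (iii)).
- *Randomized phase*: the primary endpoint and #7 as worded in sections 1.1 and 4.2.7.

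The firm conflict is therefore in the primary endpoint and #7.

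**Step 2. Length of the off-drug tail.** Treatment ends on Day 29. Follow-up is Day 36 ± 3, so Day 39 at the latest.
- Nominal: 36 − 29 = 7 days; from a Day 3 randomization, 7/(36 − 3) = 7/33 = 21% of the period.
- Maximum: 39 − 29 = 10 days; 10/(39 − 3) = 10/36 = 28%.

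**Step 3. The wording applied to hypothetical patients.**
- *A. Normal sK+ on Day 29, hyperkalaemia rescue on Day 33.* Inside the section 2.3 period: non-responder. Outside the 4-week treatment period of section 1.2: responder.
- *B. First low-bicarbonate rescue on Day 34.* A #7 event under section 2.3; not an event if the phase ends with treatment.
- *C. Low-bicarbonate rescue on Day 10, hyperkalaemia rescue on Day 18, normal sK+ on Day 29.* The period closed on Day 10, so the Day 18 rescue does not trigger the composite rule. The endpoint wording and the treatment-policy strategy require non-response, and the undated condition in section 3.3.1 points the same way.
- *D. Hyperkalaemia rescue on Day 10, low-bicarbonate rescue on Day 18.* The period closed on Day 10, so #7 misses the event, although its estimand follows patients regardless of hyperkalaemia rescue.
- *E. Low-bicarbonate rescue on Day 10 only, normal sK+ on Day 29.* Section 3.3.1 selects potassium by visit, so the patient is a responder, as treatment policy requires. Nothing goes wrong.

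**Step 4. Possible size of path A.** The SAP gives no responder rate for potassium and no follow-up rescue rate, so the rates below are assumptions. The only design figure borrowed is 68 per arm. It reproduces from section 1.3 (0.175 v 0.39, two-sided 0.05, 80% power, pooled variance): [1.960 × √(2 × 0.2825 × 0.7175) + 0.842 × √(0.175 × 0.825 + 0.39 × 0.61)]² / 0.215² = 67.6, rounded up to 68. This point does not dispute it.

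Let p be the Day 29 responder proportion and f the share of those responders rescued off drug. The counted proportion is p(1 − f), and the odds ratio is computed from the counted proportions.
- 80% SZC v 40% placebo, f = 0: (0.80/0.20)/(0.40/0.60) = 6.00.
- Same, f = 1% in both arms: (0.792/0.208)/(0.396/0.604) = 5.81. Patients reclassified: 68 × 0.80 × 0.01 = 0.5 SZC and 0.3 placebo.
- Same, f = 10% SZC and 2% placebo: (0.72/0.28)/(0.392/0.608) = 3.99. Patients reclassified: 5.4 SZC and 0.5 placebo.
- 60% v 40%: 2.25 falls to 2.23 and 1.82 under the same two settings.

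The range runs from negligible to material, and the document does not say where in it the trial lies.

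**The case against.** The strongest reply is that the endpoint itself is expressed over the randomized phase. Section 2.3 says its periods differ from the design terms, and section 1.2 separates follow-up from the 4-week treatment period. On that reading a Day 33 rescue never enters the primary endpoint. This shows a conflict between the endpoint wording and the estimand bullet. It does not resolve it, because the bullet uses the section 2.3 name exactly and nothing says that rescue counting stops at Day 29.

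The condition in section 3.3.1, read plainly, catches the later rescue in path C. That stands as evidence of intent, but it contradicts the period wording and, having no window, leaves path A open.

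Placing Visit 8 under Randomized has a legitimate safety use, since treatment-emergent events run to 7 days after the last dose. That supports a follow-up period for safety summaries, but not the same period for counting efficacy rescues.

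The affected group may also be small. The estimands tie rescue to sK+ of at least 6.0 mmol/L, so path A needs a rise from 5.0 or below within about a week, and Table 1 has no scheduled visit between Visits 7 and 8. Path C needs both kinds of rescue in that order. This stands.

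A reader might infer that closing the period at rescue also discards later Day 29 values, for the primary endpoint and for #1, #2, #3 and #5, and hence that every patient with a low-bicarbonate rescue is affected. The documents do not support this. Sections 3.3.1 and 3.3.2 select Visit 7 values by visit, and no sentence drops values after the period closes. Endpoints #1 to #6 also use other, undefined labels. For #4 and #6 both rescues are handled while on treatment, so closure at rescue does not conflict there.

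**Conclusion.** The definition is wrong as written for counting rescues. Taken literally, it makes off-drug rescues after Day 29 primary failures and #7 events, and it lets a rescue of one kind hide a later rescue of the other kind despite the treatment-policy strategy. Other SAP passages conflict with this or leave it open; none cures it.

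The conclusion rests on the primary estimand and #7 using the section 2.3 name in its defined sense. Loss of Day 29 values would need the further assumption that the period also selects data, which the SAP does not state.

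The number of patients affected cannot be derived from the document and may be small. A definite bias against SZC should not be inferred either: the direction is plausible, but the odds-ratio shifts above rest wholly on assumed rates. Early termination does not remove the point. The primary analysis is still planned, and in a smaller trial each misclassified patient weighs more.

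**What to change.** In section 2.3, define an efficacy window for counting rescues. It starts at randomization and ends at the Visit 7 assessment, or at the scheduled Day 29 date if Visit 7 is missing. It ends earlier only for withdrawal of consent, last contact or death, and not for rescue of either kind. The fixed Day 29 end is needed because, with Visit 7 missing, last contact could be Visit 8, which would bring the off-drug week back in.

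Use one label for this window in the primary endpoint, in every intercurrent-event bullet (including sensitivity analysis (iii)) and in endpoint #7, replacing the four variants and *randomized phase*. Keep the time from the end of the window to Visit 8 as a separate follow-up period for safety summaries, and label Visit 8 in Table 1 accordingly.

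The cost is SAP wording and one derived-period variable, made before the data are analysed. Sample size, data collection and the clinical rules for giving rescue are unchanged; only the counting window changes.

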3 PRIMARY AND SECONDARY VARIABLES

3.1 Time Points and Visit Windows

For all populations, assessments will be assigned to visits and analysis periods for categorical summaries as follows:

- Assessments with missing data and assessments marked "Not Done" will be considered as providing a missing response and are not permitted to be assigned to a visit window.
- The worst value (e.g. out of reference range preferred to within range; abnormal preferred to normal) will be used in each window. If multiple assessments fall within the same window with equal value, then the first non-missing will be used for the summary.

Scheduled day and visit window during the open-label period in Table 1 are with respect to the first dose of open-label study treatment. Baseline is defined as measurements taken at the screening visit on day 1 of the study.

Visit	Scheduled Day of Visit	Analysis Period	Protocol Visit Windows	Visit title in TFLs	Analysis Visit Windows
Visit 1	1	Screening/ Open-Label	Day 1	Visit 1 (Baseline)	Day 1
Visit 2	2	Open-Label	Day 2*	Visit 2	Day 2*
Visit 3	2 or 3	Randomized	Days 2 – 3*	Visit 3 (Randomization)	Days 2 – 3*
Visit 4	8	Randomized	Days 7 – 9	Visit 4	Days 4 – 11
Visit 5	15	Randomized	Days 14 – 16	Visit 5	Days 12 – 18
Visit 6	22	Randomized	Days 21 – 23	Visit 6	Days 19 – 25
Visit 7	29	Randomized	Days $28 - 30$	Visit 7 (EOT)	Days 26 – 32
Visit 8	36	Randomized	Days 33 – 39	Visit 8 (Follow-up)	Days 33 - 39

 Table 1 Definition of visit windows

* Assessments conducted on day 2 and day 3 will be assigned to visit 2 or 3 based on the nominally entered visit on the eCRF.

3.2 Subject Disposition

Screen failures are defined as subjects who consent to participate in the clinical study but fail inclusion/exclusion criteria and are not entered into the open-label correction phase. Individuals who do not meet the criteria for participation in this study (screen failure) may be rescreened after >2 weeks if screen failure was due to not meeting inclusion criterion #3 (POCT K+ level >5 mmol/L to \leq 5.9 mmol/L and POCT bicarbonate levels between 16-20 mmol/L inclusive prior to the first SZC dose on study Day 1) and/or met exclusion criterion #24 (If the participant has evidence of Coronavirus disease 2019 (COVID-19) within 2 weeks prior to screening). Further, participants who failed, due to not meeting inclusion criteria #3 may be rescreened more than once at investigator's discretion if sK+ and bicarbonate obtained during routine patient care subsequent to the last rescreening are consistent with study entry criteria. Rescreen participants will be assigned the same participant number as in the initial screen so that each participant will appear once in disposition summaries.

3.3 Efficacy Variables

3.3.1 Potassium

Whole blood samples will be analyzed locally using POCT devices to generate K+ for the purposes of study inclusion, dose adjustments, and monitoring. Samples drawn at the same timepoints will be prepared and shipped to the central laboratory for analysis of sK+. In the event that hemolysis or other artifacts are suspected based on the reported POCT K+ result, the blood samples must be re-drawn to confirm the result and only the confirmatory sample result will be reported.

The primary endpoint will use the central laboratory sK+ measurement from Visit 7 if available and no use of rescue medication for hyperkalaemia has occurred. Missing measurements at Visit 7 will be imputed as follows:

(i) If Visit 7 central laboratory sK+ is missing

Visit 6 (or an unscheduled assessment which occurs between visits 6 and 7) central laboratory sK+ will be used in its place under the principle of last observation carried forward (LOCF). If multiple measurements are available, the closest measurement to the scheduled date of Visit 7 will be used.

(ii) If central laboratory sK+ is missing for Visits 6 and 7

sK+ will be replaced by POCT values adjusted to reflect the mean difference between POCT and sK+ values from all available (including screening, baseline and unscheduled visits) paired laboratory samples in both treatment groups. The mean difference will be estimated using a summary statistic of the difference in all pairs and will not adjust for baseline characteristics. If a Visit 7 POCT value is available the adjusted value for this will be used unless missing, in which case the adjusted Visit 6 POCT will be used. If an unscheduled POCT assessment which occurs between visits 6 and 7 is available, then the closest POCT assessment to the scheduled date of visit 7 will be used.

(iii) No sK+ or POCT K available for Visits 6 or 7

The subject will be classified as non-evaluable for primary and secondary efficacy endpoints which include sK+ measurements in their definition.

Normokalaemia is defined as $3.5 \le sK+ \le 5.0$ and hyperkalaemia is defined as sK+ > 5.0 where the sK+ value used will be the result of the imputation approach described above.

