4.2.7.2 Primary Efficacy Analysis – Sensitivity Analyses

Three sensitivity analyses will be pre-specified to be conducted for the primary efficacy endpoint. Upon review of the trial data, additional post-hoc or subgroup analyses may be performed.

- Primary analysis as described above. In addition to randomized treatment, the originally specified logistic regression model would have included: race, gender, age at baseline (<65, ≥65), CKD stage at baseline (3, 4), diabetes status (Yes, No), POCT bicarbonate level at entry (16-18, 19-20), POCT type (i-STAT, Piccolo) and baseline use of RAASi therapy (Yes, No) as independent factors. Due to the early termination of the study only POCT type will be included as an independent factor.
- (ii) Primary analysis as described above but conducted in the PPS.
- (iii) The intercurrent event strategy will be altered to describe the treatment effect in a COVID-19 pandemic-free world.

- Discontinuation of treatment not related to the COVID-19 pandemic (Treatment policy strategy, i.e. regardless of the intercurrent event).
- Discontinuation of treatment related to the COVID-19 pandemic (Hypothetical strategy, i.e. assume response is missing).
- Use of rescue therapy for hyperkalaemia at any point during the randomizedwithdrawal period (Composite variable strategy, i.e. considered to be nonresponse).
- Use of rescue therapy for low bicarbonate at any point during the randomized placebo-controlled period (Treatment policy strategy, i.e. regardless of the intercurrent event).
- Death prior to Day 29 (Visit 7) not related to the COVID-19 pandemic (Composite variable strategy, i.e. considered to be non-response).
- Death prior to Day 29 (Visit 7) related to the COVID-19 pandemic (Hypothetical strategy, i.e. considered to be non-response).
- Subject lost to follow-up prior to Day 29 (Visit 7) irrespective of relationship to COVID-19 pandemic (Hypothetical strategy, i.e. assume response is not evaluable).
- Subject with no sK+ or POCT K measurement at visit 6 or visit 7 irrespective of relationship to COVID-19 pandemic (Hypothetical strategy, i.e. assume response is not evaluable).

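### SAP 3.3.1 and the primary estimand in 4.2.7.1 classify the same patients differently, most clearly a death before Visit 6, and no order of precedence is stated

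*SAP*

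**What the plan says.** **SAP 3.3.1 (Potassium).** The section opens with the value to be used: "The primary endpoint will use the central laboratory sK+ measurement from Visit 7 if available and no use of rescue medication for hyperkalaemia has occurred". It does not say what a rescued patient's result is. Three rules for a missing Visit 7 value follow.

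- Rule (i): "Visit 6 (or an unscheduled assessment which occurs between visits 6 and 7) central laboratory sK+ will be used in its place", as last observation carried forward.
- Rule (ii): adjusted point-of-care values are used when central values are missing at both visits.
- Rule (iii), for a patient with neither kind of potassium value at those two visits, reads: "The subject will be classified as non-evaluable for primary and secondary efficacy endpoints which include sK+ measurements in their definition".

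None of the three makes an exception for death or rescue.

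**SAP 4.2.7.1 (Primary Efficacy Analysis).** Missing potassium is referred to 3.3.1, and non-evaluable responses are left out of the logistic regression. The endpoint requires that no hyperkalaemia rescue was used at any point in the randomized phase. The intercurrent-event list counts such rescue as non-response. It also contains "Death prior to Day 29 (Visit 7) (Composite variable strategy, i.e. considered to be non-response" and "Subject lost to follow-up prior to Day 29 (Visit 7) (Hypothetical strategy, i.e. assume response is not evaluable". A further bullet makes a patient with no potassium at Visit 6 or 7 not evaluable, which repeats rule (iii). The list has no order of precedence.

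**SAP 4.2.7.2, sensitivity analysis (iii).** This is meant to describe a pandemic-free world. One bullet reads "Death prior to Day 29 (Visit 7) related to the COVID-19 pandemic (Hypothetical strategy, i.e. considered to be non-response".

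**The concern.** Whether a patient is No or Non-evaluable decides whether that patient enters the primary model. For some patients the SAP gives both answers, so the choice passes to whoever programs the derivation. Following the estimand alone does not settle it, because its no-potassium bullet sits beside the death and rescue bullets and overlaps both.

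The primary test also opens the hierarchy in 4.2.7, so its result decides whether any secondary endpoint is formally tested. The three primary sensitivity analyses in 4.2.7.2 add POCT type, restrict to the per-protocol set, or change the COVID-related strategies. None sets non-evaluable patients to No, so none would show how much the choice matters. They also remain in force: section 6 cancels the analyses in 4.2.7.4, 4.2.7.5 and section 5, but not those in 4.2.7.2.

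**Working it through.** **1. The rules side by side**

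| Patient | 3.3.1 | 4.2.7.1, no-potassium bullet | 4.2.7.1, other text |
|---|---|---|---|
| Dies before Visit 6 | (iii): non-evaluable | not evaluable | death: No |
| Dies after a normal Visit 6 value | (i): carried forward, can be Yes | does not apply | death: No |
| Rescued for hyperkalaemia, no usable Visit 6/7 potassium | (iii): non-evaluable | not evaluable | rescue: No; the definition rules out Yes |
| Lost after a Visit 6 value | (i): evaluable | does not apply | loss: not evaluable |

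The first row is the cleanest. By Table 1 in 3.1 the Visit 6 analysis window opens on Day 19, so a patient who dies before then can have no value for either visit.

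**2. COVID-related death in sensitivity analysis (iii).** The label is hypothetical but the coding is non-response. A death not related to COVID has a composite label and the same coding. For deaths, the analysis therefore does not separate the two causes.

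**3. The plan's own sample size.** Inputs from 1.3: 0.175 v 0.39, two-sided alpha 0.05, power 80%. With pooled variance and no continuity correction:

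n = [1.960 × √(2 × 0.2825 × 0.7175) + 0.842 × √(0.175 × 0.825 + 0.39 × 0.61)]² / 0.215² = 67.6, so 68 per group, as stated. Also 136/0.92 = 148.

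These rates are for the bicarbonate response. They supply the arm size used below but say nothing about the primary response rate.

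**4. Effect of the two codings.** All response and drop counts are assumptions. With treatment as the only factor, the logistic odds ratio is that of the 2×2 table:

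- OR = (R_S × F_P)/(F_S × R_P), where R and F are responders and non-responders on SZC (S) and placebo (P)
- SE(ln OR) = √(1/R_S + 1/F_S + 1/R_P + 1/F_P), and z = ln OR / SE

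The SAP names the model but not the test statistic; the Wald test is used here. Dropping k_S and k_P non-responders multiplies the OR by [F_S/(F_S − k_S)] × [(F_P − k_P)/F_P]. The direction thus depends on which arm loses the larger share of its non-responders.

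68 per arm, 48 v 34 responders (F_S = 20, F_P = 34):

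| Dropped SZC / placebo | OR | p |
|---|---|---|
| None (all counted No) | 48×34/(20×34) = 2.40 | 0.015 |
| 2 / 7 | 48×27/(18×34) = 2.12 | 0.047 |
| 4 / 4 | 48×30/(16×34) = 2.65 | 0.011 |
| 7 / 2 | 48×32/(13×34) = 3.48 | 0.002 |

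An assumed 20 per arm, because the study ended early and the SAP does not give the number randomized:

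| Table | OR | p |
|---|---|---|
| 15/20 v 8/20 | 15×12/(5×8) = 4.5 | 0.029 |
| 15/20 v 8/16 (4 placebo failures dropped) | 15×8/(5×8) = 3.0 | 0.13 |

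**The case against.** **Rescue.** A reader might infer that 3.3.1 drops every patient rescued before Visit 6. It does not. Rule (iii) applies only when neither a central nor a point-of-care value exists for Visits 6 or 7. Section 4.2.1 lists rescue as a reason for stopping treatment, but stopping treatment is not stopping visits, and 4.2.7.1 handles discontinuation by treatment policy. The endpoint definition prevents a rescued patient from being a Yes, and the no-rescue condition at the head of 3.3.1 can be read as a gate on the rules below it. All of this stands and favours No. It does not close the gap, because 3.3.1 never states the rescued patient's result. Section 2.3 also ends the randomized analysis period at rescue, which leaves open whether later values count.

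**Direction.** A reader might also infer that early rescue falls mainly on placebo, so that dropping these patients shrinks the effect. The SAP gives no rescue or death rates by arm. The 4/4 and 7/2 rows show the odds ratio rising.

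**Size.** The 20-per-arm example crosses 0.05 only because 4 of 20 placebo patients are assumed to be failures with no Visit 6/7 potassium. Few deaths may occur in a 28-day randomized period. That stands, and it limits the severity.

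**What is not answered.** Death before Visit 6, death or loss after Visit 6, and the COVID-death bullet remain contradictory on any reading.

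**Conclusion.** The concern holds as a missing order of precedence. Death before Visit 6 is a direct contradiction that no other text resolves. Rescue without usable Visit 6/7 potassium is a weaker ambiguity. Carry-forward after death, carry-forward after loss, and COVID-related death in sensitivity analysis (iii) are further inconsistencies; the last affects that sensitivity analysis only.

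The SAP does not allow the size or direction to be stated. Under the assumed counts, reclassifying nine of 136 patients moves the odds ratio from 2.40 to between 2.12 and 3.48. In the assumed smaller trial, dropping four patients moves p from 0.029 to 0.13. If no randomized patient falls into these categories, the primary result is the same under either reading. This should be fixed: it determines who enters the primary analysis, and correcting it is nearly free.

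**What to change.** 1. In both 3.3.1 and 4.2.7.1, state that hyperkalaemia rescue during the randomized phase up to Visit 7, or death before Visit 7, is classified as No first. Rules (i) to (iii) and the no-potassium bullet then apply only to the remaining patients. Editing 3.3.1 alone would leave the conflicting bullet in place. The Visit 7 limit is needed because the period in 2.3 can run on into follow-up.
2. Reconcile the lost-to-follow-up bullet with rule (i). One option is to limit the bullet to patients with no Visit 6/7 potassium; what matters is that a single rule is stated.
3. In sensitivity analysis (iii), make the coding of COVID-related death match its hypothetical label, that is, not evaluable.
4. For combined secondary endpoints #4 and #6, which rule (iii) also governs, align the while-on-treatment strategy for rescue with definitions that require no rescue.
5. Optional check: rerun the primary model with the remaining non-evaluable patients set to No.

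The cost is SAP wording, a few lines of derivation code and, if item 5 is taken up, one more model run. The wording should be settled before treatment codes are available to those programming the endpoint. If that point has passed, the report should state which classification was used and how many patients it affected in each arm.
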